6.2. Preparation/Handling/Storage/Accountability

1. The investigator or designee must confirm appropriate temperature conditions have been maintained during transit for all study interventions received and any discrepancies are reported and resolved before use of the study intervention.
2. Only participants enrolled in the study may receive study intervention and only authorized site staff may supply or administer study intervention. All study interventions must be stored in a secure, environmentally controlled, and monitored (manual or automated recording) area in accordance with the labeled storage conditions with access limited to the investigator and authorized site staff. At a minimum, daily minimum and maximum temperatures for all site storage locations must be documented and available upon request. Data for nonworking days must indicate the minimum and maximum temperatures since previously documented for all site storage locations upon return to business.
3. Any excursions from the study intervention label storage conditions should be reported to Pfizer upon discovery along with any actions taken. The site should actively pursue options for returning the study intervention to the storage conditions described in the labeling, as soon as possible. Once an excursion is identified, the study intervention must be quarantined and not used until Pfizer provides permission to use the study intervention. Specific details regarding the definition of an excursion

and information the site should report for each excursion will be provided to the site in the IP manual.

4. Any storage conditions stated in the SRSD will be superseded by the storage conditions stated on the label.
5. Study interventions should be stored in their original containers.
6. Site staff will instruct participants on the proper storage requirements for take-home study intervention.
7. The investigator, institution, or the head of the medical institution (where applicable) is responsible for study intervention accountability, reconciliation, and record maintenance (ie, receipt, reconciliation, and final disposition records), such as the IPAL or sponsor-approved equivalent. All study interventions will be accounted for using a study intervention accountability form/record. All study intervention that is taken home by the participant, both used and unused, must be returned to the investigator by the participant. Returned study intervention must not be redispensed to the participants.
8. Further guidance and information for the final disposition of unused study interventions are provided in the IP manual. All destruction must be adequately documented. If destruction is authorized to take place at the investigator site, the investigator must ensure that the materials are destroyed in compliance with applicable environmental regulations, institutional policy, and any special instructions provided by Pfizer.

Upon identification of a product complaint, notify the sponsor within 1 business day of discovery as described in the IP Manual.

6.2.1. Preparation and Dispensing

Within this protocol, preparation refers to the investigator site activities performed to make the IP ready for application or dispensing to the participant/caregiver by qualified staff.

Dispensing is defined as the provision of IP, concomitant treatments, and accompanying information by qualified staff member(s) to a healthcare provider, participant, or caregiver in accordance with this protocol. Local health authority regulations or investigator site guidelines may use alternative terms for these activities.

The IP will be dispensed in a blinded fashion using an interactive response technology (IRT) system at Day 1/Baseline, Week 1, Week 2 and Week 4 visits. A qualified staff member will dispense the IP via unique container numbers on the cartons provided, in quantities appropriate for the study visit schedule and the treatable % BSA.

For doses to be applied at home, the participant or caregiver should be instructed to maintain the product in its original package provided throughout the course of dosing and return the product and its original package (including empty, partial used and unused tubes) to the site at the next study visit.

IP will be assigned to participants at the Day 1 visit once the participant is successfully randomized through the IRT system. The investigator, appropriate delegate or site personnel will access the IRT system at screening and all subsequent IP dispensing visits to enter information including, but not limited to, the participants height, weight and % affected BSA to receive correct tube numbers to be dispensed to the participant. Alternatively, the tool to standardize the IP need calculation across participants and study sites may be provided by the sponsor.

The calculation of treatable BSA is described in [Section 8.1.2.3](#) and [Section 8.1.4.3](#) for AD and psoriasis respectively.

All tubes of investigational product dispensed or returned will be recorded and documented.

6.2.2. Investigational Product Accountability

The investigator site must maintain adequate records documenting the receipt, use, loss, or other disposition of the IP supplies. All investigational products will be accounted for using a drug accountability form/record. All tubes of the IP must be returned to the investigator by the participant at every visit and at the end of the trial.

The participant will be asked to bring all dispensed IP (including empty, partially used and unused tubes) at every 'compliance check' visit; participants will be asked to bring dosing diary to the clinic at every clinic visit. All previously dispensed IP tubes will be retained by the site. For each participant, IP tubes with caps will be weighed individually or collectively by the study site before dispensing and after return and the weights will be recorded. The sponsor will use the recorded weights to estimate usage (eg, mg/cm²/application) for each participant. Note that the weight recorded on the IP label is a nominal weight and not an exact weight of the IP and tube. Detailed drug accountability records, including tube weights measured in the clinic, will be maintained by study staff for each participant.

The original IP accountability log, or equivalent document, must be accurately completed, signed by the Investigator, and retained at the study site (with a copy supplied to the Sponsor) when the study is complete.

6.2.3. Destruction of Investigational Product Supplies

For all IP returned to the investigator by the participant, the investigator will maintain the returned supply until destruction is authorized.

The sponsor or designee will provide guidance on the destruction of unused investigational product (eg, at the site). If destruction is authorized to take place at the investigator site, the investigator must ensure that the materials are destroyed in compliance with applicable environmental regulations, institutional policy, and any special instructions provided by Pfizer, and all destruction must be adequately documented.

Further guidance and information for the final disposition of unused study interventions are provided in the IP manual.

6.3. Measures to Minimize Bias: Randomization and Blinding

6.3.1. Allocation to Study Intervention

Allocation of participants to treatment groups will proceed through the use of an IRT system (IWR). The site personnel (study coordinator or specified designee) will be required to enter or select information including but not limited to the user's ID and password, the protocol number, and the participant number. The site personnel will then be provided with a treatment assignment, randomization number, and DU or container number when study intervention is being supplied via the IRT system. The IRT system will provide a confirmation report containing the participant number, randomization number, and DU or container number assigned. The confirmation report must be stored in the site's files.

Study intervention will be dispensed at the study visits summarized in the [SoA](#).

Returned study intervention must not be redispensed to the participants.

The study-specific IRT reference manual and IP manual will provide the contact information and further details on the use of the IRT system.

6.3.2. Breaking the Blind

The IRT will be programmed with blind-breaking instructions. In case of an emergency, the investigator has the sole responsibility for determining if unblinding of a participant's treatment assignment is warranted. Participant safety must always be the first consideration in making such a determination. If the investigator decides that unblinding is warranted, the investigator should make every effort to contact the sponsor prior to unblinding a participant's treatment assignment unless this could delay further management of the participant. However, discussion with the Sponsor in advance of unblinding is not required. If a participant's treatment assignment is unblinded, the sponsor must be notified within 24 hours after breaking the blind. The date and reason that the blind was broken must be recorded in the source documentation and CRF.

The study-specific IRT reference manual and IP manual will provide the contact information and further details on the use of the IRT system.

6.4. Study Intervention Compliance

The participant and/or a caregiver will apply IP at home or during in-clinic visits as specified in the [SoA](#). The participant and/or caregiver will be instructed to complete the Dosing Diary starting with the first dose applied in the clinic on Day 1 through Week 6 (each time IP is applied) for the IP doses applied at home. Participants will be instructed to refrain from dosing at home on the day of the in-clinic visit, and are to bring to the clinic all used, partially used and empty IP tubes in their original containers for weighing, at each visit.

Participant compliance with IP will be assessed on visits identified in the [SoA](#). Compliance will be assessed by review of the participant/caregiver completed Dosing Diary and by weighing of the returned IP tubes. The difference in weight(s) of the returned IP tubes will be used to estimate the doses applied. Source documents will be placed in the participant's study file. Deviation(s) from the prescribed dosage regimen should be recorded in the CRF.

From Day 1 through Week 6 visit, non-compliance is defined as less than 80% or more than 120% of IP applications. If non-compliance is identified, or even if a few dose applications are missed or over-applied, then, participants will be re-trained on the importance and the process of proper IP application. If non-compliance persists, the investigator, in consultation with the Sponsor, may withdraw any participant from the study for reasons of non-compliance with the dosing regimen. Investigators should indicate on the appropriate CRF page noncompliance with study intervention and provide an explanation.

Inventory control of all IPs must be rigorously maintained throughout the duration of the study until all medication has been accounted for and/or returned to the sponsor. Any discrepancies noted between drug dispensing records and the drug inventory must be reported to Pfizer.

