7.2. Participant Discontinuation/Withdrawal from the Study

A participant may withdraw from the study at any time at his/her own request. Reasons for discontinuation from the study include the following:

- Refused further follow-up;
- Lost to follow-up;
- Death;
- Study terminated by sponsor.

At the time of discontinuing from the study, if possible, an early discontinuation visit should be conducted. See the [SoA](#) for assessments to be collected at the time of study discontinuation and follow-up and for any further evaluations that need to be completed.

The early discontinuation visit applies only to participants who are enrolled/randomized and then are prematurely withdrawn from the study. Participants should be questioned regarding their reason for withdrawal. The participant will be permanently discontinued both from the study intervention and from the study at that time.

If a participant withdraws from the study, he/she may request destruction of any remaining samples taken and not tested, and the investigator must document any such requests in the site study records and notify the sponsor accordingly.

If the participant withdraws from the study and also withdraws consent (see [Section 7.2.1](#)) for disclosure of future information, no further evaluations should be performed and no additional data should be collected. The sponsor may retain and continue to use any data collected before such withdrawal of consent.

Lack of completion of all or any of the withdrawal/early termination procedures will not be viewed as protocol deviations so long as the participant's safety was preserved.

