9.1. Estimands and Statistical Hypotheses

9.1.1. Estimands for AD

The primary estimand will be the population average treatment effect on percent change from baseline in EASI score relative to vehicle at 6 weeks in the absence of prohibited medication without regard to compliance. All observations after the initiation of prohibited medication will be set to missing. Missing data from all causes, including post-randomization prohibited medication use will be imputed in the PF-07038124 arms using a copy to control method (ie, missing data in 0.01% QD regimen will be imputed from the distribution of participants on QD vehicle). Participants with inadequate compliance will have their recorded EASI scores used as is in the analysis. The population-based treatment effect will be the differences in the mean change from baseline in treatment arm compared to the vehicle.

The secondary estimand will be the estimated population average treatment effect on the rates of IGA response (participants with a score of 0 or 1 and a 2 point or greater decrease from baseline) at Week 6 relative to vehicle without regard to compliance with IP in the absence of prohibited medication. This is a composite estimand where success is defined as achievement of an IGA response as defined above while remaining on study, providing data and not taking prohibited medication; lack of compliance or adverse events will not be counted as a failure. The population-based treatment effect will be the differences in the proportions of success in each treatment arm compared to the corresponding vehicle. EASI 75 and other EASI scores will be treated in a similar manner.

All other secondary continuous clinical endpoints will be analyzed using the primary estimand, while all other secondary categorical clinical endpoints will be analyzed using the secondary estimand described above. CCI

Other estimands may be used for some of the primary and secondary endpoints as a means to examine the robustness of the results and to compare to available literature as needed. Details of these analyses will be presented in the Statistical Analysis Plan (SAP).

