9.1.2. Estimands for Psoriasis

The primary estimand will be the population average treatment effect on change from baseline in PASI scores at Week 6 relative to vehicle without regard to compliance in the absence of prohibited medication. Measurements after the initiation of prohibited medication will be censored and treated as missing data. Missing data due to censoring, study withdrawal or other reasons will have data imputed using a copy to control method (ie, missing data in 0.01% QD regimen will be imputed from the distribution of participants on QD vehicle) assuming these participants no longer receive an efficacy benefit from the IP but rather, have a response similar to participants assigned to vehicle. Participants with inadequate compliance will have their recorded PASI scores used as is in the analysis. The population-based treatment effect will be the differences in the mean change from baseline in each treatment arm compared to the corresponding vehicle.

The secondary estimand will be the population average treatment effect on the PGA response rate (percentage of participants with a score of clear (0) or almost clear (1) and ≥ 2 point improvement from baseline at Week 6 relative to vehicle without regard to compliance with IP in the absence of prohibited medication. This is a composite estimand where success is defined as achievement of a PGA response while remaining on study, providing data and not taking prohibited medication; lack of compliance or adverse events will not be counted as a failure. The population-based treatment effect will be the differences in the proportions of successes in each treatment arm compared to the corresponding vehicle.

All other key secondary continuous clinical endpoints will be analyzed using the primary estimand, while all other key secondary categorical clinical endpoints will be analyzed using the secondary estimand described above. CCI

Other estimands may be used for some of the primary and secondary endpoints as a means to examine the robustness of the results and to compare to available literature as needed. Details of these analyses will be presented in the SAP.

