### 2.1.1. Primary Estimand(s)

The primary estimands of this study will use the treatment policy strategy and estimate the treatment difference without the benefit of additional prohibited medications during treatment and regardless of participant compliance with the IP dosing. This estimand (Estimand 1) for AD and Psoriasis are defined according to the primary objectives and are in alignment with the primary endpoints.

For AD, it includes the following 4 attributes:

- Population: Participants with mild or moderate AD as defined by the inclusion and exclusion criteria; without the benefit of receiving prohibited medications during treatment and regardless of compliance.
- Variable: Percent change from baseline in EASI total score at Week 6.
- Intercurrent event(s): A) Prohibited medication – all scores in participants who receive prohibited medication post randomization will be omitted from the analysis and treated as missing scores. Missing scores will be imputed based on the assumption that participants do not benefit from the IP treatment. B) Withdrawal and all other events leading to missing data will be treated similarly assuming participants have efficacy values similar to control participants. C) Inadequate compliance – participants data will be used as recorded.
- Population-level summary: The percent change from baseline mean difference between treated and vehicle in EASI score.

For Psoriasis, it includes:

- Population: Patients with mild to moderate plaque psoriasis as defined by the inclusion and exclusion criteria of the study who do not take prohibited medications during treatment and regardless of compliance.
- Variable: Change from baseline PASI score at Week 6.
- Intercurrent events: A) Prohibited medication – all scores in participants who receive prohibited medication post randomization will be omitted from the analysis and treated as missing scores. Missing scores will be imputed based on the assumption that participants do not benefit from the IP treatment. B) Withdrawal and all other events leading to missing data will be treated similarly as in A). C) Inadequate compliance – participants data will be used as recorded.
- Population-level summary: The mean difference between treated and vehicle control arms of the change from baseline PASI score.

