### 2.1.2. Secondary Estimand(s)

Estimand E2: This estimand is intended to provide a population level estimate of the treatment effect of the IP on a binary responder endpoint; without the benefit of additional prohibited medications and regardless of a participant compliance with the IP dosing.

All continuous secondary endpoints will be analyzed descriptively and using estimand E1 described above, when appropriate.

All binary secondary endpoints will be analyzed descriptively and using estimand E2 described above, when appropriate.

- Population: Participants with mild or moderate AD or Psoriasis as defined by the inclusion and exclusion criteria; without the benefit of receiving prohibited medications during treatment and regardless of compliance.
- Variables: Proportion of participants achieving IGA score of clear (0) or almost clear (1) and a reduction from baseline of  $\geq 2$  points at Week 6 for AD; Proportion of participants with PGA score clear (0) or almost clear (1) (on a 5-point scale) and  $\geq 2$  points improvement from baseline at Week 6 for Psoriasis; and other categorical secondary endpoints.
- Inter-current Events: A) Prohibited medication – response will be considered negative for participants who receive prohibited medication post-randomization. B) Withdrawal and all other events leading to missing data will be treated similarly assuming that participants no longer receive benefit from the IP and hence will be treated as failure for endpoint above. C) Inadequate compliance – participants data will be used as recorded.
- Population level summary:

The difference in proportions between IP treated and vehicle response rates.

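### Protocol 6.4 lets a discretionary withdrawal for persistent non-compliance turn an obtainable Week 6 outcome into an imputed value or a failure, although both estimands disregard compliance; a low-priority, cheap change avoids this

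*Protocol*

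**What the plan says.** **Compliance.** Protocol 6.4 defines non-compliance as under 80% or over 120% of applications and calls for re-training first. Then: "If non-compliance persists, the investigator, in consultation with the Sponsor, may withdraw any participant from the study".

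**Leaving the study.** Protocol 7.2 says of participants withdrawn early: "The participant will be permanently discontinued both from the study intervention and from the study at that time". An early discontinuation visit is held if possible. The same section refers to the Schedule of Activities (SoA) for "assessments to be collected at the time of study discontinuation and follow-up and for any further evaluations that need to be completed". Its list of reasons for leaving the study does not mention non-compliance.

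**Stopping IP only.** Protocol 7.1 treats this as different from leaving the study: the participant has the Early Termination (ET) visit and remains for follow-up. Section 7.2.1 likewise keeps in the study anyone who asks to stop IP.

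**Estimands under non-compliance.** Protocol 9.1.1: "Participants with inadequate compliance will have their recorded EASI scores used as is in the analysis". Section 9.1.2 says the same for psoriasis: "Participants with inadequate compliance will have their recorded PASI scores used as is in the analysis". For the responder estimand, success is a response achieved "while remaining on study, providing data and not taking prohibited medication; lack of compliance or adverse events will not be counted as a failure".

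**Estimands under withdrawal.** SAP 2.1.1, for E1: "Withdrawal and all other events leading to missing data will be treated similarly assuming participants have efficacy values similar to control participants". SAP 2.1.2, for E2, assumes that "participants no longer receive benefit from the IP and hence will be treated as failure for endpoint above". SAP 5.3.1 makes an exception only for data missing because of COVID-19.

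**Window.** SAP Appendix 2.1 assigns assessments to visits by study day. Week 6 is Day 37 to 57.

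**The concern.** The same behaviour can lead to two different analysis values. A participant who under-applies or over-applies and stays in the study contributes the Week 6 score as recorded. A participant with the same behaviour who is withdrawn under 6.4, with no assessment in the window, contributes a vehicle-based value (E1, active arm) or a failure (E2, either arm). What separates them is a decision by the investigator and sponsor, taken because of non-compliance, and sites may take it differently.

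This also sits badly with the rest of the plan. Someone who asks to stop IP altogether is kept and followed under 7.2.1, while someone applying three quarters of the doses can be removed. The SAP amendment stopped censoring data collected after early drug discontinuation, on the ground that the estimand ignores non-compliance. Section 6.4 can prevent such data from being collected at all.

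At stake are primary and key secondary outcomes that could have been obtained, in arms planned at 21 and 12 evaluable participants.

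**Working it through.** **1. Planning inputs (Protocol 9.2.1, 9.2.2).** Atopic dermatitis (AD): difference 50, SD 48, 28 randomized and 21 evaluable per arm. Psoriasis: difference 4.5, SD 4.2, 16 and 12 per arm. These reproduce the plan's figures. Two-sample t-test power is 90.9% (stated about 90%) and 81.5% (stated about 80%). Pooled-variance power for two proportions is 65.9% for IGA (stated 66%) and 61.9% for PGA (stated 61.9%). Allowing for 25% dropout, 21/0.75 = 28 and 12/0.75 = 16. No planning figure is in dispute.

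**2. When the outcome is lost.** Scheduled compliance checks are at Weeks 1, 2, 4 and 6.
- Found at Week 1, persisting at Week 2: ET at about Day 13–17, before the window.
- Found at Week 2, persisting at Week 4: ET at about Day 27–31, before the window.
- Found at Week 4, re-checked at Week 6: nothing is lost.
- Any ET visit from Day 37 to 57 can serve as Week 6.

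**3. Whether Follow-up rescues the case.** Follow-up is 28–35 days after the last dose and includes EASI/IGA or PASI/PGA. With the last dose on the visit day:
- Week 2 stop: 13 + 28 = 41 to 17 + 35 = 52, inside the window.
- Week 4 stop: 27 + 28 = 55 to 31 + 35 = 66, inside only on Days 55–57.

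An earlier last dose moves this forward. A last dose on Day 24 gives Day 52–59.

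**4. Earlier scores.** The sample imputation code in SAP Appendix 4 uses only baseline and the Week 6 score, with the model fitted to vehicle. Under that code, improvement seen at Weeks 1 to 4 does not inform the imputed value.

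**5. E1 shift per withdrawn active-arm participant.** Expected shift = fraction of planned effect kept × planned difference / number randomized per arm. Standard error (SE) of the difference = SD × √(2/n), with n evaluable per arm: 48 × √(2/21) = 14.8 and 4.2 × √(2/12) = 1.71. The fraction kept is not in the documents; the values below are assumptions.

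| Fraction kept | EASI, percentage points | in SE | PASI, points | in SE |
|---|---|---|---|---|
| 0 | 0 | 0 | 0 | 0 |
| 25% | 0.45 | 0.03 | 0.07 | 0.04 |
| 50% | 0.89 | 0.06 | 0.14 | 0.08 |
| 100% (bound) | 50/28 = 1.8 | 0.12 | 4.5/16 = 0.28 | 0.16 |

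With all randomized participants in the SE (12.8 and 1.48), the bound is 0.14 and 0.19 SE. Missing vehicle-arm scores are imputed from the vehicle arm under missing at random, so the copy-to-control shift arises only in the active arm.

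**6. E2 shift per lost responder.** 1/28 = 3.6 percentage points (AD); 1/16 = 6.3 (psoriasis).

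**7. Illustration with several cases.** Assume 10% of each AD arm is lost this way. E1 then targets 0.9 × 50 = 45. With the scores recorded and 50% to 100% of the effect kept, it would be 45 + 0.1 × 25 = 47.5 to 45 + 0.1 × 50 = 50.

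**The case against.** A reader might infer that 6.4 contradicts the estimands, or that the plan counts non-compliance as failure after saying it will not. The documents do not support this. Non-compliance and withdrawal are listed as separate intercurrent events, each with its own rule. Success under E2 expressly requires staying in the study and providing data, so a withdrawn participant fails that requirement and not one about compliance. Vehicle-based imputation is a deliberate, stated assumption.

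Other objections have force:
- The clause is permissive and comes after re-training, persistence and sponsor consultation. A 25% dropout allowance is planned.
- The pointer to follow-up in 7.2 may be read as requiring the Follow-up visit, which would rescue a Week 2 stop and some Week 4 stops. Protocol 8.3.1 sets adverse event collection at a minimum of 28 days after the last dose, which suggests that later contact is intended.
- The E1 shift is small and conservative.
- Stopping IP but keeping the visit gives a score well after the last dose, not the outcome under continued imperfect use. At Day 43 this is 43 − 17 = 26 to 43 − 13 = 30 days after a Week 2 stop, or 43 − 31 = 12 to 43 − 27 = 16 days after a Week 4 stop.
- Participants who stop IP for adverse events under 7.1 also go to ET and follow-up with no named Week 6 visit, so changing 6.4 alone is uneven.

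All of this limits the size and priority, but none of it closes the gap. Section 7.2 also says that the participant leaves the study at that time, so its follow-up wording is ambiguous. Section 8.3.1 covers adverse events, not efficacy scores, and its collection period ends if consent for further information is withdrawn. Pre-specifying both rules does not explain why non-compliance should be a reason to stop collecting the outcome.

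**Conclusion.** The point holds as a design weakness, not as an inconsistency. Section 6.4 allows a discretionary decision, triggered by the factor both estimands disregard, to make an obtainable Week 6 outcome missing. This happens only when no assessment falls in Day 37 to 57.

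The number of such participants cannot be derived from the documents and may be zero. The expected E1 shift is toward no effect. Its bound of 1.8 EASI percentage points or 0.28 PASI points per active-arm participant requires the full planned effect to be kept, which is unlikely. It is probably under 0.1 SE, but that rests on the assumed 25% to 50%. The E2 figures apply only to a participant who would have been a Week 6 responder. A failure can arise in either arm, so the direction of the E2 effect is not fixed.

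A reader might also infer that every such withdrawal loses the endpoint, or that the trial's conclusions are at risk. Neither follows: late ET visits count as Week 6, Follow-up visits may fall in the window, and the effect per participant is small. This is a cheap improvement of low priority.

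**What to change.** In Protocol 6.4, replace the permission to withdraw from the study with wording to this effect: persistent non-compliance may lead to discontinuation of IP only; the participant stays in the study, has the ET visit, and completes the Week 6 (Day 43) EASI/IGA or PASI/PGA assessment and the Follow-up visit, unless consent is withdrawn. Week 6 must be named, because 7.1 alone leads only to ET and follow-up. Preferably require the same Week 6 assessment of other IP discontinuers under 7.1, so that those stopping for adverse events are treated alike.

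The cost is a short amendment and one or two visits already in the SoA for each participant concerned. After a Week 2 stop, Week 6 (Day 41–45) and Follow-up can be combined: a last dose on Day 13 allows any of Days 41–45, and one on Day 17 allows Day 45. After a Week 4 stop on the visit day they are separate visits. These participants may attend poorly, so the change reduces this source of missing data without removing it.
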